### **6.2.3 End of trial and follow-up period**

#### **6.2.3.1 End of treatment visit**

End of Treatment Visit (0-7 days after permanent discontinuation of study drugs)

Refer to the [Flow Chart](#) for details. The patient must return all study drugs, and the site must document the reason for permanent discontinuation of study medication. If permanent discontinuation of study drug occurs during a scheduled visit, examinations as defined for EOTV should be performed instead of the examinations for the scheduled visit.

Blood samples for soluble biomarkers (for all patients), PK and immunogenicity (for patients on BI 836845 regimen) must be obtained.

In patients who are experiencing disease progression at EOTV of the phase II part, a fresh tumor biopsy should be performed from those with appropriate informed consent.

#### **6.2.3.2 Follow-up**

This follow-up period is aimed for collection of additional AE and PD information. Refer to the [Flow Chart](#) and [Appendix 10.5](#) for details.

Blood samples for soluble biomarkers, PK and immunogenicity (for patients on BI 836845 regimen) must be obtained at FU1.

## **Phase I part**

All patients should have a follow-up visit 42 days (+7days) after the permanent discontinuation of study drugs.

Proprietary confidential information.

© 2016 Boehringer Ingelheim International GmbH or one or more of its affiliated companies. All rights reserved.

This document may not - in full or in part - be passed on, reproduced, published or otherwise used without prior written permission.

## Phase II part

*Follow-up 1 (42 + 7 days after permanent discontinuation of study drug)*

Every patient should complete the first follow-up visit. Refer to the [Flow Chart](#) for details.

### *Additional follow-up visits*

Additional follow-up visits should be performed at scheduled tumor assessment according to the Flow chart.

The follow-up period for every Phase II patient will end at the earliest of the following events:

- Disease progression
- Start of a new anti-cancer therapy
- Lost to follow-up
- Withdrawal of consent
- Death

### 6.2.3.3 Observation period

## Phase I part

There is no observation period in the phase I part.

## Phase II part

All patients will be followed-up for Overall Survival every 90 days after the last follow-up visit (as specified in [Section 6.2.2.2](#)) until death or completion of the whole trial (as specified in [Section 6.2.3.4](#)) whichever occurs earlier. During this period only information on patient vital status and subsequent anti-cancer treatment(s) will be collected. The investigator may report SAE if s/he becomes aware of it.

The following information should be collected from patient's notes or by telephone contact (a formal visit is not required). The investigator/site staff should make at least three tries to obtain the information if a phone contact is conducted.

- Date of contact and method of contact
- Further anticancer treatment
- Death
- Lost to follow-up
- Withdrawal of consent

A snapshot of observation period data may be requested at any time. Following the primary analysis, the collection of observation period data may be reduced in frequency or stopped as appropriate, as decided and communicated by the Trial Clinical Monitor.

Proprietary confidential information.

© 2016 Boehringer Ingelheim International GmbH or one or more of its affiliated companies. All rights reserved.

This document may not - in full or in part - be passed on, reproduced, published or otherwise used without prior written permission.

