##### **Phase II part**

The end of the phase II part of the trial will be when the last patient has completed the first follow-up visit.

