#### 7.3.2.1 Other analyses

Stratified Cox proportional hazards model will be used to compute the hazard ratio of overall survival (OS) for BI 836845 in combination with exemestane and everolimus vs. exemestane and everolimus alone. Kaplan-Meier curves of OS will be calculated. Stratified log-rank test with nominal p-value will also be performed to compare the survival curves. OS will be analyzed twice. The first analysis will be performed at the time of primary PFS analysis. The second analysis will take place at the time of trial completion when all patients permanently discontinued the study drug and when the last patient completed the first follow up (FU1) visit.

For all patients (Phase I and Phase II, separately) with measurable target lesions, the maximum percent decrease since baseline in sum of the longest diameters of all target lesions and the percent change over time will be explored descriptively and graphically. Other further endpoints will be analysed descriptively.

Proprietary confidential information.

© 2016 Boehringer Ingelheim International GmbH or one or more of its affiliated companies. All rights reserved.

This document may not - in full or in part - be passed on, reproduced, published or otherwise used without prior written permission.

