7 PLANNED ANALYSES

The labelling and display format of statistical parameters will follow BI standards [\(7\)](#).

Unless otherwise specified, outputs will be displayed separately for each part of the trial.

Descriptive statistics for continuous variables will generally contain N (number of patients in that patient set with non-missing values), Mean, Standard Deviation, Minimum (Min), 25th percentile (Q1), Median, 75th percentile (Q3), Maximum (Max). In general, means, standard deviations, medians, Q1 and Q3 will be presented to one more decimal place than the raw data. Minima and maxima will be presented to the same number of decimal places as the raw data.

For time-to-event analysis tables, the set of statistics is: number of patients [N (%)], Number of patients with event [N (%)], Number of patients censored [N (%)], <Time to event> [months] followed by Q1 (25th percentile), Median, Q3 (75th percentile). If not specified otherwise, the duration as well as time to event will be displayed in months.

Tabulations of frequencies for categorical data will include all possible categories and will display the number of observations in a category as well as the percentage (%) relative to the respective treatment group total. Percentages will be rounded to one decimal place.

In general a category “missing” will be displayed, if there are missing data for the corresponding variable. Percentages will also generally be based on all patients in the respective patient set whether they have non-missing values or not.

The primary analysis will include all treated (Phase Ib) or randomised patients (Phase II), following the ITT approach (as specified in [Section 6.3](#)).

The analyses for the primary endpoint of PFS as well as best overall response, OR, time to OR, duration of OR, DC, duration of DC, time to progression, tumor shrinkage, tumor size as well as the [REDACTED] will be based on data obtained until November 25th 2016. A sensitivity analysis for the primary endpoints PFS will be performed using all data. Analyses of other RECIST based endpoints will also only utilise data obtained from assessments scheduled until November 25th 2016. For overall survival all available data will be used.

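### If observation-period vital-status collection is stopped after the primary analysis, the second overall-survival analysis censors mainly progressed patients and the late Kaplan-Meier curves are too high

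*Protocol*

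**What the plan says.** Protocol 6.2.3.3 (Phase II part) gives the default: "All patients will be followed-up for Overall Survival every 90 days after the last follow-up visit", continuing "until death or completion of the whole trial". The same section then allows an exception once the primary analysis is done: "the collection of observation period data may be reduced in frequency or stopped as appropriate". The Trial Clinical Monitor decides and communicates this. No criterion is given, and nothing is said about OS if the option is used. A snapshot of observation-period data may be requested at any time but is not required.

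Protocol 6.2.3.2 defines who enters the observation period: "The follow-up period for every Phase II patient will end at the earliest of the following events", namely progression, new anti-cancer therapy, loss to follow-up, withdrawal of consent or death. Patients without these events keep their treatment visits, the first follow-up visit (FU1, 42 to 49 days after the last study drug) and scheduled tumour assessments. Section 6.2.3.4 adds: "The end of the phase II part of the trial will be when the last patient has completed the first follow-up visit".

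Protocol 7.3.2.1 plans two OS analyses, each with Kaplan-Meier curves, a stratified Cox hazard ratio and a nominal stratified log-rank p-value. The first is at the primary PFS analysis. For the other: "The second analysis will take place at the time of trial completion when all patients permanently discontinued the study drug", and the last patient has completed FU1.

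SAP section 7 fixes 25 November 2016 as the data limit for PFS and the other RECIST-based endpoints, then states: "For overall survival all available data will be used".

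**The concern.** If collection is stopped, a patient's censoring depends on her disease status. A woman who has progressed is censored on the stop date. A woman who has not is still seen, and her death would still be recorded. A woman who progresses later is seen until about FU1 and is then lost. Progression predicts death, so the censoring is informative. Kaplan-Meier and Cox methods assume that it is not.

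At stake are the late part of both OS curves and any late median read from them. Protocol 7.2 names overall survival among the endpoints on which conclusions about efficacy will rest. A reader of the final report could not tell from the curve that its tail rests mainly on patients selected for not having progressed.

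**Working it through.** **Inputs from the protocol (section 7.6).** 150 patients, 1:1, 12.5 per month for A = 12 months; exponential PFS with medians 10.8 and 7.8 months (λ = 0.064 and 0.089); primary analysis at 90 PFS events; 20%, 25% or 30% permanently censored.

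**The plan's own figure.** Let F(T) be the protocol's accrual formula for the proportion with a PFS event by month T. Solving 150 × (1 − d) × F(T) = 90 gives T = 24.92, 27.95 and 32.57 months for d = 20%, 25% and 30%. The protocol states 24.9, 27.9 and 32.5, so its durations reproduce. They give the range of earliest stop dates S.

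**Who would still be followed.** 150 × (1 − F(S)) is 37.5, 25.8 and 21.5 patients without a PFS event at S = 24.9, 30 and 32.5 months, ignoring permanent censoring. Only this minority would remain under observation.

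**Where bias can start.** The last patient enters at month 12, so at the stop date everyone has at least S − 12 months of follow-up: 24.9 − 12 = 12.9 to 32.5 − 12 = 20.5 months. Before that point there is no bias.

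**Assumptions not in the documents.** Post-progression survival is exponential with a median of 12, 18 or 24 months. The second OS analysis is at S + 24 months. Deaths occur only after progression. FU1 falls about 1.4 months after progression.

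**Complete follow-up, closed form.** With μ = ln 2 / (post-progression median), OS(t) = (λe^(−μt) − μe^(−λt)) / (λ − μ). For control, an 18-month median and t = 36: λ = 0.0889, μ = 0.0385, and (0.0889 × 0.25 − 0.0385 × 0.0408) / 0.0504 = 0.41.

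**Selective follow-up.** Simulation with 300,000 patients per scenario; progressed patients are censored at S and later progressors at FU1. OS at 36 months, complete / selective:

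| Stop (months) | Post-progression median | Control | Experimental |
|---|---|---|---|
| 24.9 | 12 | 0.279 / 0.504 | 0.358 / 0.599 |
| 24.9 | 18 | 0.410 / 0.617 | 0.476 / 0.695 |
| 24.9 | 24 | 0.505 / 0.692 | 0.561 / 0.752 |
| 30 | 12 | 0.282 / 0.414 | 0.357 / 0.509 |
| 30 | 18 | 0.410 / 0.534 | 0.476 / 0.612 |
| 30 | 24 | 0.502 / 0.613 | 0.562 / 0.683 |
| 32.5 | 12 | 0.280 / 0.369 | 0.358 / 0.469 |
| 32.5 | 18 | 0.409 / 0.493 | 0.475 / 0.572 |
| 32.5 | 24 | 0.504 / 0.579 | 0.563 / 0.651 |

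The excess runs from 0.579 − 0.504 = 7.5 points to 0.599 − 0.358 = 24.1 points.

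At 24 months the excess is much smaller. For medians of 15 to 24 months it is 3 to 5 points with a stop at about 25 months, about 1 point at 30 and about 0.3 points at 32.5. With a 12-month median and the 24.9-month stop it reaches 0.636 − 0.572 = 6.4 points.

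A common cut-off at S = 30 (18-month median) gives control OS of 0.609 at 24 months, equal to complete follow-up, and no estimate from 30 months on.

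**Hazard ratio** (S = 30, 18-month median): 0.838 complete, 0.802 common cut-off, 0.787 selective. Shorter follow-up accounts for 0.838 − 0.802 = 0.036 and selection for 0.802 − 0.787 = 0.015. Across the nine scenarios selective and common cut-off differ by 0.013 to 0.023. With identical arms the three values are 0.995, 0.988 and 0.990.

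**The case against.** The strongest reply is that the visible text cannot show that the safeguard is missing. The public SAP does not show its OS definition or censoring rule, yet OS rules exist: Table 6.6: 1 imputes death dates for the OS analysis. The SAP also follows protocol amendment 3 of 15 December 2016, written after recruitment and xentuzumab were stopped, whereas the supplied protocol ends at amendment 2. Whether the stopping option and the second OS analysis survived is unknown. This stands. It makes the point conditional but does not remove it: the SAP's sentence on OS exempts it from the RECIST data limit, and no supplied passage sets another common date. Section 4.2 still has the report revised after the last patient completes, and section 7.8.1 says everolimus and exemestane continued, so a later OS look with some patients on treatment is plausible.

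Second, stopping is a permission. The default is contact every 90 days to the end, reduced frequency alone need not bias anything, and a snapshot could be taken before the second analysis. This also stands: the bias arises only if collection is actually stopped.

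Third, OS is exploratory, with no formal testing, and 36-month survival is not a planned estimate. That limits the consequence, although Kaplan-Meier OS curves are planned and would show the distortion.

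A reader might also infer that after the stop only unprogressed patients remain at risk. That is not exact: later progressors remain at risk until about FU1, and the calculation allows for this.

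**Conclusion.** The point holds conditionally. If observation-period collection is stopped, and the second OS analysis then uses all available data without a common date, the late OS curves are biased upward in both arms. At 36 months the excess is about 7 to 24 points; at 24 months it is 0 to 5 points for post-progression medians of 15 to 24 months; before about month 13 to 20 it is nil.

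These sizes rest on assumed post-progression survival, an assumed second analysis 24 months after the stop, and the planned 150-patient design. Recruitment was halted on 28 October 2016, so the realised size may differ. The upward direction held in every scenario.

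A reader might infer a material bias in the treatment comparison. The figures do not support that: the hazard ratio is about 0.79 against 0.80 with a common cut-off, and near 1 when the arms do not differ. Most of the gap from 0.84 under full follow-up is shorter follow-up, which a common cut-off would not restore. Nor do the documents show that collection was in fact stopped, or that the plan has no OS censoring rule.

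**What to change.** First check amendment 3 and the SAP's OS definition and censoring rule. If either already sets a common OS date or a vital-status check of all patients before the second analysis, no change is needed.

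Otherwise state one of the following in protocol 7.3.2.1 and SAP section 7:

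- If observation-period collection is stopped before the second OS analysis, OS for every patient, including those still on treatment, is cut off at the last date on which vital status was sought for all patients. The SAP's provision on OS data is then limited to that date.
- Or the default 90-day contact continues, or one vital-status sweep of all patients is made, up to the second OS analysis.

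The first option costs a sentence in each document. It drops a few late deaths (0.7 to 2.5 per 150 patients in the nine scenarios; for example 54.9 − 53.8 = 1.1 with a stop at 30 months and an 18-month median) and gives no OS estimate beyond the cut-off. The second costs continued contact, by telephone or from patient notes, but keeps the later deaths: about 105 per 150 in the same scenario, against about 54 at the common cut-off.

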#### 6.2.3.4 End of Trial

##### **Phase I part**

The end of the phase I part of the trial will be when the last patient has completed the follow-up visit.

##### **Phase II part**

The end of the phase II part of the trial will be when the last patient has completed the first follow-up visit.

## 7. STATISTICAL METHODS AND DETERMINATION OF SAMPLE SIZE

### 7.1 STATISTICAL DESIGN – MODEL

Only descriptive and exploratory analyses are planned and no formal statistical testing is planned.

### 7.2 NULL AND ALTERNATIVE HYPOTHESES

As an exploratory Phase II trial, inferences about the efficacy of BI 836845 in combination with exemestane and everolimus will be based on the magnitude of the observed difference in PFS and other efficacy endpoints, e.g. objective response, overall survival, rather than a formal hypothesis testing.

### 7.3 PLANNED ANALYSES

During the Phase I part, cohorts of patients treated with BI 836845 in combination with exemestane and everolimus will be evaluated continuously based on the totality of the safety data available in order to determine the recommended phase II dose.

Efficacy analysis will include all randomised patients in the Phase II part. For the Phase I dose finding stage, PFS and objective tumor response will be summarized descriptively by cohort. No comparison will be done between cohorts.

Safety analysis will be summarized separately for patients treated in the Phase I and Phase II part of the trial. The safety profile of the Phase II part will be compared in a descriptive manner between the experimental and the control arm.

